### Development

The sample size is fixed at 934 participants in the development sample. To adequately power the regression analysis and potential exploratory analysis, we will follow recent sample size recommendations by Riley et al. [71,72] using the *pmsampsize* module in STATA 16.1 (StataCorp LLC, Texas, USA). This prediction sample size calculator is also available online: <https://riskcalc.org/pmsamplesize/>.

In order to include all prognostic factors, corresponding to Table 1 and including 2 parameters for each continuous predictor to account for potential non-linear trends, 19 parameters ( $P$ ) are needed. We will target an expected shrinkage factor ( $S$ ) of 0.9, to

reflect small optimism in predictor effect estimates, as recommended by Riley et al. [72]. We assume that the models will have a modest Nagelkerke's  $R^2$  of 25% which corresponds to a Cox-Snell  $R^2$  of 0.185.

- For the first end-point (>90 days), the event rate is 0.403 (416 events of 934), which gives a minimum required sample size ( $n$ ) of 826 (with 368 events), resulting in an event per predictor parameter (EPP) of 19.35.
- For the second end-point (>180 days), the event rate is 0.172 (161 events of 934), which results in a minimum required sample size ( $n$ ) of 826 (with 143 events) and an EPP of 7.48.
- For the third end-point (WAA/DP), the event rate is 0.108 (101 events of 934), which gives a minimum required sample size ( $n$ ) of 826 (with 90 events) and an EPP of 4.7.

Our fixed sample size exceeds these minimum requirements. Therefore, we expect our study to be adequately powered which will lead to minimal shrinkage and reliable results.

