### *External validation*

Our validation cohort has a fixed sample size of 336. To ensure unbiased and precise performance measures (e.g., calibration and discrimination), Collins et al. [73] recommend that external validation samples have a minimum of 100 events. We will adhere to this guideline when interpreting the results from the external validation.

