### *Model performance*

The predictive performance of the apparent model in the development sample will be assessed using measures of overall performance, calibration, and discrimination. Overall performance will be assessed using Nagelkerke's pseudo  $R^2$ . Calibration will be examined by plotting (calibration plot) the observed proportions of events against the predicted risks for groups defined by ranges of individual predicted risks. To quantify the performance of calibration, the calibration will be described by calibration-in-the-large (intercept) and calibration slope, with perfect calibration characterised by an intercept of 0 and a slope of 1 [37]. We will also assess the ratio of Expected to Observed cases (E/O). To explore the model's ability to discriminate those at higher risk of having an event from those at lower risk, c-statistic will be used. The c-statistic is equivalent to the area under the curve (AUC) statistic from receiver operating characteristic (ROC) curves. An index measure of 1 indicates perfect discrimination, whilst 0.5 demonstrates that the discrimination of the model is no better than by chance alone [37]. A c-statistic of 0.60–0.69 represents poor discrimination, 0.70–0.79 fair, 0.80–0.89 excellent, and  $\geq 0.90$  outstanding discrimination [80].

To decrease the possibility of overfitting the model, the amount of optimism in the model will be assessed and corrected by internal validation techniques, using bootstrap re-sampling to estimate the degree of optimism due to overfitting [81]. To adjust for this overfitting, we will use the *bsvalidation* module in STATA or similar commands in STATA or R software. The bootstrap procedure will include all modelling steps for the assessment of the model's performance. The model building will be repeated for 500 bootstrap samples [82,83]. Initially, the difference in bootstrap performance and test performance will be averaged over the 500 samples. This will

give a single estimation of the optimism of the model. Finally, this estimate will be subtracted from the estimates of the apparent model performance.

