### *External validation*

We will externally validate the models to determine the validity of predictions for workers on sick leave outside the development sample. We will use data from the MI study, which included participants from a different geographical region than the development sample. Hence, this validation is called external geographic validation. External geographic validation has been found to have higher generalisability than internal validation and is essential before a prognostic model can be applied to practice [37,84].

To assess the extent of transportability or reproducibility, we will estimate the relatedness between the development and validation samples according to Debray et al. [85]. This will be performed using two approaches. In the first approach, we will examine relatedness of the samples by estimating a binary logistic regression model (membership model), to predict the probability that a participant belongs to the development sample ("1") compared with the validation sample ("0"). The independent variables in this model will include the primary outcome (long-term sickness absence), age, sex, education level, and all the predictors from the prognostic model. Thereby, we will assess the discriminative ability of this membership model by quantifying the *c*-statistic. Low values (close to 0.5) indicate that the samples are largely the same and that the case-mix is indistinguishable between the datasets. In the second approach, we will compare the mean and standard deviation of the linear predictor of the prognostic model in the development and validation sample. A large difference in the linear predictor indicates a heterogeneity of the case-mix between the two samples.

Model performance will be tested in the external validation sample using the predictive performance statistics calculated as detailed above in the model performance section. It will be estimated using the model coefficients from the developed models to calculate the individual risk scores [86]. In addition to these performance measures, we will also assess the clinical usefulness of the prognostic models by calculating decision-curve analysis for the model. This will evaluate the ability to make better decisions with a prognostic model than without, by using a decision-curve analysis that estimates the net benefit and compares this to decision-making strategies (treat all/treat none) [82,87].

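### The membership model's in-sample c-statistic is read against 0.5, although with these sample sizes it averages about 0.57-0.58 when the case-mix is identical

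*SAP*

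**What the plan says.** The SAP's External validation section (under Statistical analysis methods) assesses relatedness in two ways. The first is a logistic model for belonging to the development rather than the validation sample. Its covariates "include the primary outcome (long-term sickness absence), age, sex, education level, and all the predictors from the prognostic model". The plan then says "we will assess the discriminative ability of this membership model by quantifying the" c-statistic, and gives the reading rule: "Low values (close to 0.5) indicate that the samples are largely the same and that the case-mix is indistinguishable between the datasets". No cut-off, interval, null reference or optimism correction is stated for this model.

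The second way compares the mean and standard deviation of the prognostic model's linear predictor between the two samples.

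The 500-resample bootstrap under Model performance is described for the prognostic models in the development sample. External validation refers back to that section only for the prognostic models' performance in the validation data.

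The sizes come from the Sample size section: "The sample size is fixed at 934 participants in the development sample" and "Our validation cohort has a fixed sample size of 336".

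**The concern.** A logistic model that is fitted and scored in the same people separates the two groups a little better than chance even when membership is unrelated to every covariate, because the coefficients adapt to noise. The expected in-sample c-statistic is therefore above 0.5 under identical case-mix, by an amount set by the number of parameters and the two sample sizes. The SAP handles this for the prognostic models but not for the membership model.

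What is at stake is interpretation. The plan uses relatedness to say whether the validation speaks to reproducibility (similar people) or transportability (different people). The bias runs one way, towards apparent difference and hence towards transportability, the stronger claim.

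**Working it through.** **Inputs.**
- Sample sizes: 934 and 336, total 1,270 (Sample size section).
- Prognostic parameters: 13 in Table 2, or 12 if the three-category depression/anxiety item takes two indicators. With non-linear terms, the Development subsection gives "including 2 parameters for each continuous predictor to account for potential non-linear trends, 19 parameters": Table 2 has six continuous predictors and 13 + 6 = 19, or 18 with two indicators.
- Membership model: add outcome and sex, since age and education are already in Table 2. This gives 14-15 parameters (linear) or 20-21 (non-linear).

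**Check of the parameter count.** The SAP's own minimum sample size reproduces: n = P / [(S - 1) ln(1 - R²/S)] with P = 19, S = 0.9 and R² = 0.185 gives 825.7, that is, the stated 826. The SAP gives no expected value for the membership c-statistic, so there is no figure of that kind to reproduce.

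**Expected in-sample c under identical case-mix, closed form.** c ≈ Φ(√[p(1/934 + 1/336)/2]), where 1/934 + 1/336 = 0.004047.
- p = 14: Φ(√0.02833) = Φ(0.1683) = 0.567
- p = 15: Φ(√0.03035) = Φ(0.1742) = 0.569
- p = 20: Φ(√0.04047) = Φ(0.2012) = 0.580
- p = 21: Φ(√0.04249) = Φ(0.2061) = 0.582

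**The same by simulation.** Both samples were drawn from one population, the logistic model was fitted by maximum likelihood, and c was computed in the fitting data. The 14- and 20-parameter rows use mixed continuous and binary predictors with assumed correlations and prevalences (2,000 replicates). The 15- and 21-parameter rows use independent normal predictors (1,000 replicates).

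| Parameters | Mean c | 95% range | Chance of c ≥ 0.60 |
|---|---|---|---|
| 14 | 0.566 | 0.543-0.592 | 0.7% |
| 15 | 0.568 | 0.543-0.594 | 0.8% |
| 20 | 0.578 | 0.552-0.606 | 5% |
| 21 | 0.581 | 0.557-0.606 | 7% |

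**Resolution near the null.** With 15 parameters, samples whose true c is 0.55 give an in-sample c averaging 0.583 (95% range 0.556-0.614). This overlaps heavily with the null range, so an observed 0.58 cannot be assigned to either case.

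**Bias when the samples do differ.** Age medians are 50.1 (cohort, n = 549) and 48.8 (MI-NAV trial, n = 514) against 45.0 (MI study). The weighted development value is (549 × 50.1 + 514 × 48.8)/1,063 = 49.5. The interquartile ranges divided by 1.349 give SDs of about 11, so the standardised difference is 4.5/11 ≈ 0.4 and age alone implies c ≈ Φ(0.4/√2) = 0.61. Adding an assumed shift in prior sick leave of 0.5 or 0.7 SD gives Φ(√(0.4² + 0.5²)/√2) = 0.675 and Φ(√(0.4² + 0.7²)/√2) = 0.716. In simulation (400 replicates, independent normal predictors) the excess of in-sample over true c was:
- true c 0.61: 0.019 (15 parameters) and 0.026 (21)
- true c 0.675: 0.011-0.016
- true c 0.716: 0.010-0.012

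**Possible corrections.** A bootstrap optimism correction, tested on 100 null data sets with 100 resamples each, brought the mean c from 0.566 to 0.522 (14 parameters) and from 0.578 to 0.524 (20 parameters), each with a 95% range of about 0.49-0.555. It removes most of the bias but does not centre on 0.50. A permutation distribution of the membership label gives the null reference directly.

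**The case against.** A reader might infer that two identical samples would be declared different under this plan. The documents do not support that. The SAP sets no cut-off, so 0.57-0.58 might well be accepted as close to 0.5. The SAP's general scale for the c-statistic starts its lowest named band at 0.60, which the null reaches in only about 1-7% of cases. That scale grades discrimination and is not offered as a threshold for relatedness, so it does not settle the reading either way.

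A reader might also infer that this one number decides between reproducibility and transportability. It does not: the linear-predictor comparison is a separate check that does not use the membership model. It sees case-mix only along the prognostic score, however, and the SAP does not define a large difference there either.

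The strongest counter-argument is that the identical-population scenario is unlikely here. Besides the age medians, the upper age limit is 67 against 60, prior-year sick leave has medians of 37.8 and 36.8 against 52.1 workdays, and entry requires at least 4 or 7 weeks of sick leave against 8. At the true c these suggest, the bias is about 0.01-0.03 and would not change a qualitative reading. This stands, with one caveat: the medians describe the full source samples. The analysed samples are restricted to musculoskeletal diagnoses and 4-12 weeks of sick leave, and may differ less.

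**Conclusion.** The point holds as a minor one. For the statistic the SAP computes, 0.5 is not the value expected under identical case-mix. That value is about 0.57-0.58, with a 95% range of roughly 0.54-0.61 across 14 to 21 parameters. An observed c up to about 0.60 cannot be distinguished from identical case-mix and could be misread as evidence of transportability. A clearly higher value would not be produced by this bias alone.

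The bias is 0.07-0.08 at the null and about 0.01-0.03 at a true c of 0.61-0.71. The prognostic models and their calibration, discrimination and decision curves are unaffected.

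The figures assume complete data, one outcome term per membership model, age and education counted once, and an intervention indicator distributed alike in both samples under the null. The non-null figures also assume roughly normal age and the stated shifts in prior sick leave.

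**What to change.** In External validation, report the membership c-statistic with a confidence interval and compare it with the distribution obtained by permuting the membership label and refitting the same model each time. This replaces the comparison with 0.5. State which position in that distribution will be read as compatible with identical case-mix. An ordinary interval around the in-sample value is centred on a biased estimate, so whether it contains 0.5 should not be the criterion.

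A bootstrap optimism-corrected c may be reported as well, noting that it averages about 0.52 under the null. The cost is one or two sentences in the SAP and a small amount of computing, with no new data.

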## Sensitivity analysis

We will perform several sensitivity analyses to assess the robustness of the findings based on our primary analyses. The results of the sensitivity analyses will either be published in the main paper or as an additional paper.

1. *Candidate predictors.* To ensure that important predictors are not missed during the development, we plan to conduct analyses by adding other important candidate predictors that are only present in the development sample and not in the validation sample. This is to determine if some of these candidate predictors improve the accuracy of the models.
2. *End-point definitions.* Since no consensus on the definition of long-term sickness absence exists, we will perform sensitivity analysis to explore the differences in model performance between varying end-points, such as >120 days and >270 days.
3. *Sick leave days adjustment.* As graded sick leave only applies in some countries (e.g., Norway and Sweden), we will also conduct sensitivity analyses where we do not adjust sick leave days for sick leave grading or percentage of contracted work hours.
4. *Full-time absenteeism.* Those who are on full-time sick leave have the highest risk of long-term disability benefits [88]. Therefore, we will undertake sensitivity analyses to evaluate the models' predictive ability to predict the end-points (>90 days and >180 days) when we only include full-time absenteeism in the calculation of these end-points.

5. *Predicting a second dialogue meeting.* Within week 26 of the sick leave process, the Norwegian Labour and Welfare Service (NAV) must summon the employee and the employer to a second dialogue meeting. The purpose of this meeting is for the parties to review the situation and create a follow-up plan for the employee's return to work. Dialogue meetings are legally mandated, and all parties are required to participate. Today, it is the NAV caseworker's assessments that form the basis for the decision on whether to hold a second dialogue meeting or not. A recent report from NAV [89] has highlighted that caseworkers use a lot of resources to assess if the second dialogue meeting should be held or not, and that they find this assessment difficult as the information base is scarce. Moreover, NAV must already by week 17 decide if a second dialogue meeting will be necessary, that is, whether the sick employee will be fit to work again within week 26 or not. Therefore, we will also explore if our model can be used to predict the risk of still being on sick leave at week 26.
6. *Inclusion criteria.* Since the duration of sick leave is an important prognosis factor of prolonged sickness absence [28], a sensitivity analysis will be performed to evaluate the predictive performance of the prognostic models after the removal of participants who had been on sick leave for more than 8 weeks at the start-point.
7. *Imputation of missing data.* Depending on how we handle missing data (multiple imputation or complete cases) as described in 'Missing data'-section, we will perform a sensitivity analysis to compare the proposed methods.
8. *External validation.* We also want to evaluate the model's predictive ability in the entire validation sample, that is, to include participants with all types of sick leave causes (e.g., mental disorders).

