MI-NAV trial [25,27]	514	Three-arm parallel RCT	Vestfold, Norway	ICPC-2	12 months	Sick leave due to MSD for at least 7 weeks (>50 % of contracted working hours). Aged 18-67 years.	Yes	Development
MI study [24]	865	Three-arm parallel RCT	Trøndelag, Norway	ICPC-2	12 months	Sick leave due to any diagnoses for at least 8 weeks (>50 % of contracted working hours). Aged 18-60 years.	Yes	External validation

Abbreviations: ICPC-2, International Classification of Primary Care 2nd version; MI, motivational interviewing; MSD, musculoskeletal disorders; RCT, randomised controlled trial.

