### *Validation sample*

We will externally validate the models using data from all arms of a second RCT (MI study) [24]. This study evaluated the effect of motivational interviewing on return to work in a social security setting using a parallel group design. Participants aged 18 to 60 who had been on sick leave for more than 8 weeks were recruited through the NAV system. Individuals who were not employed or pregnant were excluded. This trial comprised 865 participants, median age 45.0 (IQR, 37.0-52.0) years, who had been on sick leave at a median of 52.1 (IQR, 40.4-65.6) workdays the previous year. The results from this trial have not been published yet.

The inclusion criteria for all studies are pragmatic and unrestricted, indicating that they are likely to be representative of the target population. We plan to use data from all arms (intervention and control) of the RCTs.

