### **Source population**

Our prognostic models will be focused on information collected between the initial 4-12 weeks of a sick leave spell due to MSDs. As such, participants of each dataset will be eligible if they at baseline were:

- On sick leave due to a musculoskeletal diagnosis within the musculoskeletal (L) chapter of ICPC-2 [26].
- On sick leave for at least 50% of their contracted work hours for 4-12 consecutive weeks.

Individuals on sick leave for more than 12 weeks at baseline were excluded.

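### Sensitivity analysis 8 plans no separate result for workers on leave for non-musculoskeletal causes, and the pooled figures dilute any loss of performance in that group

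*SAP*

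**What the plan says.** The models are built for musculoskeletal leave. Under Source population, the SAP restricts every dataset to people who were "On sick leave due to a musculoskeletal diagnosis within the musculoskeletal (L) chapter of ICPC-2", with leave graded at 50% or more for 4 to 12 weeks. It adds: "Individuals on sick leave for more than 12 weeks at baseline were excluded".

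The validation data come from the MI study. Table 1 gives its entry criterion as "Sick leave due to any diagnoses for at least 8 weeks", and the Validation sample section says "This trial comprised 865 participants". The Sample size section states: "Our validation cohort has a fixed sample size of 336". It also cites guidance whose authors "recommend that external validation samples have a minimum of 100 events", and says this will guide interpretation.

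For the main external validation, "Model performance will be tested in the external validation sample using the predictive performance statistics" listed under Model performance: Nagelkerke's R², calibration plot, intercept and slope, E/O and c-statistic. Decision curves are added.

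Item 8 under Sensitivity analysis then plans to "evaluate the model's predictive ability in the entire validation sample, that is, to include participants with all types of sick leave causes", with mental disorders as the example. Neither item 8 nor the External validation methods plan a breakdown by diagnosis group or an estimate for the non-musculoskeletal participants alone.

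**The concern.** The musculoskeletal participants already have their own result from the main validation. The only new information in item 8 lies in the people added, and nothing is planned that describes them directly. A pooled estimate mixes the known result with the unknown one, in proportions set by this trial's diagnosis mix.

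The SAP itself gives reason to expect different behaviour in the added group. Table 2 includes pain intensity and a fear-of-movement item taken from a musculoskeletal screening tool, and their value for leave due to mental disorders is open.

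What is at stake is the interpretation of a secondary analysis. A moderately good pooled c-statistic or slope could be read as showing that the models work across diagnoses when they rank people poorly outside musculoskeletal leave.

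**Working it through.** **Inputs.** From the SAP: 336 (Sample size, External validation), 865 (Validation sample), and development events of 416, 161 and 101 among 934 (Sample size, Development). The counts 336 and 865 are stated, so there is no formula to reproduce. All performance values below are assumptions for illustration.

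**Step 1: composition.** 336/865 = 38.8%, and 865 − 336 = 529 (61.2%). These are bounds. The 336 were selected on duration and grade as well as diagnosis, so the 529 may include musculoskeletal workers outside the 4-12 week window. If that window also applies in item 8, fewer than 865 are used. The non-musculoskeletal group is therefore at most 529. The documents do not give its actual size.

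**Step 2: E/O can be worked back.** With expected (E) and observed (O) counts for both analyses, the added group's ratio is (E pooled − E musculoskeletal)/(O pooled − O musculoskeletal). Example with equal event rates, and E/O of 1.00 in the 336 and 0.70 in the 529: the pooled value is (336 × 1.00 + 529 × 0.70)/865 = 706.3/865 = 0.82. Working back, (706.3 − 336)/529 = 0.70. The failure is diluted but recoverable.

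**Step 3: the c-statistic cannot.** It is an average over pairs of one person with and one without the event. With equal event rates and a 336:529 mix, the pairs divide as follows:

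- both musculoskeletal: 0.388² = 0.151
- both from the added group: 0.612² = 0.374
- one from each group: 2 × 0.388 × 0.612 = 0.475

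So pooled c = 0.151 × c(musculoskeletal) + 0.374 × c(added) + 0.475 × c(cross). The planned reports give the pooled and musculoskeletal values, which leaves one equation with two unknowns. Nearly half the pairs are cross-group and measure discrimination within neither group. The pooled slope is likewise affected by differences in predicted risk between the groups.

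**Step 4: illustrations.** A large-sample simulation (865,000 people, mixed 336:529) took the model as correct in the musculoskeletal group: c 0.76, slope 1.00, E/O 1.00. The linear predictor (LP) there was normal with SD 1.1 and mean −0.25 (A, D) or 0 (B, C). In the added group:

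- A: LP mean −0.25, SD 1.1; true log-odds 0.4 × LP
- B: LP mean −1.0, SD 0.8; true log-odds −0.4 + 0.4 × LP
- C: LP mean −1.2, SD 0.6; true log-odds −1.2 for everyone
- D: LP mean −0.25, SD 1.1; true log-odds 0.6 + LP

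| Case | c added | c pooled | slope added | slope pooled | E/O added | E/O pooled |
|---|---|---|---|---|---|---|
| A | 0.62 | 0.67 | 0.40 | 0.60 | 0.94 | 0.97 |
| B | 0.59 | 0.69 | 0.40 | 0.72 | 0.93 | 0.97 |
| C | 0.50 | 0.69 | 0.00 | 0.79 | 1.07 | 1.03 |
| D | 0.76 | 0.75 | 1.00 | 0.98 | 0.79 | 0.86 |

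From A to C the added group's c-statistic falls from 0.62 to 0.50, while the pooled value rises from 0.67 to 0.69 and the pooled slope from 0.60 to 0.79. B and C share the same musculoskeletal and pooled c-statistics (0.76 and 0.69) but differ in the group of interest.

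**Step 5: what a separate estimate would rest on.** If development event rates held (assumption), the 529 would have 529 × 416/934 = 236, 529 × 161/934 = 91 and 529 × 101/934 = 57 events. The SAP prints a rate of 0.403 beside 416 of 934, which is 0.445. At 0.403 the first figure would be 213, still above 100. In all 865 the second and third would be about 149 and 93. In the 336 the three would be about 150, 58 and 36. By the square-root rule, intervals in 529 are √(865/529) = 1.28 times as wide as in 865.

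**The case against.** The strongest reply is that item 8 has a different purpose. The SAP introduces its sensitivity analyses as checks on robustness and nowhere says that item 8 tests transport to other diagnoses. Performance in a mixed social-insurance population is a legitimate target, and a pooled sample addresses it. That stands, and is why the pooled analysis should stay. It does not remove the need for the separate figures, because the pooled result depends on this trial's diagnosis mix.

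Three stronger readings are tempting, and the documents do not support them.

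- **That pooling could hide miscalibration altogether.** With E/O of 1.20 in the 336 and 0.87 in the 529 at equal event rates, the pooled value is (403.2 + 460.2)/865 = 1.00. A reader might infer that both errors disappear. They do not: the 1.20 is reported as the main validation, and subtraction gives 460.2/529 = 0.87. The pooled slope of 0.60 in case A would also be a warning in itself. Case C needs no discrimination together with lower predicted risk in the added group, and the documents show neither.
- **That item 8 drops the 4-12 week limit and uses all 865.** The item explains its wider sample by diagnosis alone, and Source population applies the duration and grade criteria to each dataset. Nothing lifts them. The most that can be said is that the SAP should confirm it.
- **That the result would be used to extend the models beyond musculoskeletal leave.** The objectives, Source population and Discussion all confine them to musculoskeletal disorders.

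The loss of precision is also a fair objection. On the assumed rates, end-point 2 drops from about 149 events in 865 to 91 in 529, crossing the 100-event guideline. This calls for caution in reading the separate estimate. The larger pooled count does not supply the missing information about the added group.

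**Conclusion.** The point holds as a low-severity improvement. Item 8 recounts the musculoskeletal participants and plans no estimate for the people it adds. Any loss of performance in them is diluted. E/O is roughly recoverable by comparison with the main validation, but the c-statistic and calibration slope are not.

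The non-recoverability follows from how these measures are built and does not rest on assumed values. The sizes do: the simulated performance figures are illustrative, 38.8% and 529 are bounds, and the event counts assume development rates. No primary estimate is affected.

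**What to change.** Keep the pooled all-cause analysis in item 8 and add three things.

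1. Report the c-statistic, calibration slope, intercept and E/O, with confidence intervals, for the non-musculoskeletal participants alone, beside the musculoskeletal and pooled results. Give participants and events for each group.
2. State that the 4-12 week and 50% criteria of Source population still apply, so that diagnosis is the only thing that changes.
3. State that, for any end-point with fewer than 100 events in the non-musculoskeletal group, the result is exploratory. On the assumed rates this would be end-points 2 and 3.

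The cost is a few lines of SAP text and one filter on data already held. The price in precision is intervals about 28% wider than with 865, and more once the duration filter is applied. Because the pooled analysis is retained, nothing now planned is lost.
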